5.4.2.2. Estimands

The following describes the attributes of the estimands for the secondary efficacy endpoints.

Study Intervention:

- Experimental: guselkumab
- Control: placebo

Population: participants between 18 to 75 years (inclusive) with diagnosis of SSc according to ACR and EULAR 2013 criteria with a disease duration of \leq 36 months (defined as time from first non-Raynaud phenomenon manifestation), and mRSS \geq 10 to \leq 22 units

Variables and Population-level Summary:

Variable (Endpoint)	Population-level Summary
Change from baseline in mRSS at Week 52	Difference in LSMS of change from baseline in mRSS at Week 52 between guselkumab vs placebo
The proportion of participants who experience worsening of mRSS at Week 24	Odds ratio of proportion of participants who experience worsening of mRSS at Week 24 between guselkumab vs placebo
The proportion of participants who experience worsening of mRSS at Week 52	Odds ratio of proportion of participants who experience worsening of mRSS at Week 52 between guselkumab vs placebo
The proportion of participants achieving a score of 0.6 in ACR CRISS at Week 24	Odds ratio of proportion of participants who achieve a score of 0.6 in ACR CRISS at Week 24 between guselkumab vs placebo
The proportion of participants achieving a score of 0.6 in ACR CRISS at Week 52	Odds ratio of proportion of participants who achieve a score of 0.6 in ACR CRISS at Week 52 between guselkumab vs placebo
Change from baseline in FVC and percent predicted FVC at Week 24	Difference in LSMS of change from baseline in FVC and % predicted FVC at Week 24 between guselkumab vs placebo
Change from baseline in FVC and percent predicted FVC at Week 52	Difference in LSMS of change from baseline in FVC and % predicted FVC at Week 52 between guselkumab vs placebo
Change from baseline in the measured absolute DLCO and the derived percent predicted DLCO at Week 24	Difference in LSMS of change from baseline in the measured absolute DLCO and the derived % predicted DLCO at Week 24 between guselkumab vs placebo

Variable (Endpoint)	Population-level Summary
Change from baseline in the measured absolute DLCO and the derived percent predicted DLCO at Week 52	Difference in LSMs of change from baseline in the measured absolute DLCO and the derived % predicted DLCO at Week 52 between guselkumab vs placebo
Change from baseline in digital ulcer counts at Week 24	Difference in LSMs of change from baseline in digital ulcer counts at Week 24 between guselkumab vs placebo
Change from baseline in digital ulcer counts at Week 52	Difference in LSMs of change from baseline in digital ulcer counts at Week 52 between guselkumab vs placebo
Change from baseline in HAQ-DI score at Week 24	Difference in LSMs of change from baseline in HAQ-DI score at Week 24 between guselkumab vs placebo
Change from baseline in HAQ-DI score at Week 52	Difference in LSMs of change from baseline in HAQ-DI score at Week 52 between guselkumab vs placebo

Intercurrent events and their corresponding strategies:

The intercurrent events for all key secondary endpoints at Week 24 are the same as those in the primary estimand, as follows:

1. A prohibited change in SSc medication (for details, see [Appendix 11](#))
2. Discontinuation of study intervention due to lack of efficacy or an AE of Systemic Sclerosis

As rescue medication is available for participants after Week 24, an additional intercurrent event is defined for secondary efficacy endpoints at Week 52.

3. Initiation of rescue medication after Week 24

Intercurrent events 1, 2 and 3 are all handled by the **composite strategy** to assume that the occurrence of intercurrent events indicates an unfavorable outcome. For continuous endpoints, the change from baseline will be zero; and for binary endpoints, the participants are considered as not achieving an improvement (ACR CRISS score ≥ 0.6) or experiencing worsening (an increase from baseline ≥ 5 points and $\geq 20\%$ in mRSS).

5.4.2.3. Analysis Methods

For continuous endpoint as change from baseline in mRSS at Week 52, an MMRM model with treatment group, baseline mRSS, stratification factors (presence of ILD [yes, no] and baseline anti-topoisomerase I antibody status [positive, negative]), visit, treatment group by visit interaction, and baseline mRSS by visit interaction as fixed effects will be applied. The estimates of the treatment difference between guselkumab and placebo will be provided by the difference in the least squares means (LSMs), as well as the 2-sided 80% and 95% CIs for the differences and p-values.

For continuous endpoints other than change from baseline in mRSS at Week 52, an MMRM model with treatment group, baseline value of the endpoint, stratification factors (presence of ILD [yes, no], baseline mRSS (low [≥ 10 to ≤ 15], high [≥ 16 to ≤ 22]) and baseline anti-topoisomerase I antibody status [positive, negative]), visit, treatment group by visit interaction, and baseline value of the endpoint by visit interaction as fixed effects will be applied. The estimates of the treatment difference between guselkumab and placebo will be provided by the difference in the least squares means (LSMs), as well as the 2-sided 80% and 95% CIs for the differences and p-values. The degree of freedom will be calculated as the error degrees of freedom for the model minus the number of extra random effects estimated.

An unstructured covariance matrix for repeated measures within a participant will be used. In case of lack of convergence, empirical structured covariances will be used in the following order until convergence is reached: 1) Toeplitz 2) first order Autoregressive Moving Average. If the normality assumption is in question, an appropriate transformation will be used.

For binary endpoints such as proportion of participants achieving an ACR CRISS score of 0.6, a logistic regression model that includes factors for treatment group and stratification factors (presence of ILD [yes, no], baseline mRSS (low [≥ 10 to ≤ 15] or high [≥ 16 to ≤ 22]) and baseline anti-topoisomerase I antibody status [positive, negative]) will be applied provide the odds ratios, p-values, as well as the 2-sided 80% and 95% CIs for comparisons between guselkumab and placebo.

5.4.2.4. Supplementary Analysis for Change from Baseline in MRSS at Week 52

The analysis is performed on the supplementary estimand of change from baseline in mRSS at Week 52 as in Section 5.4.2.2. The similar estimand as described in Section 5.4.2.2 is built except that intercurrent event “initiation of rescue therapy medication after Week 24” will be handled by treatment policy. An MMRM model similar as described in Section 5.4.2.3 is built and 80% CIs will be calculated.

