3. SAMPLE SIZE DETERMINATION

There is lack of positive placebo-controlled trials in dcSSc.

Taking into account the following 4 Phase 2/3 placebo-controlled trials (see [Table 2](#)) in SSc with mRSS results reported in the ClinicalTrials.gov registry, a reasonable estimate of the standard deviation (SD) to be used in the sample size calculation of this study has been taken as 8.0.

Table 2: Standard deviations of mRSS in Referenced Phase 2/3 Placebo-controlled Trials in SSc

Trial	Treatment group		Placebo group	
	N	Estimated SD	N	Estimated SD
A Double-Blind, Randomised, Placebo-controlled Trial Evaluating Efficacy and Safety of Oral Nintedanib Treatment for at Least 52 Weeks in Patients With Systemic Sclerosis Associated Interstitial Lung Disease (SSc-ILD) (NCT02597933)	288	4.582	288	4.412
A Phase 3, Multicenter, Randomized, Double-Blind, Placebo-Controlled, Parallel-Group Study to Assess the Efficacy and Safety of Tocilizumab Versus Placebo in Patients With Systemic Sclerosis (NCT02453256)	104	8.169	106	8.142
A Phase 2/3, Multicenter, Randomized, Double-blind, Placebo-controlled Study To Assess The Efficacy And Safety Of Tocilizumab Versus Placebo In Patients With Systemic Sclerosis (NCT01532869)	43	8.266	41	8.933

Trial	Treatment group		Placebo group	
	N	Estimated SD	N	Estimated SD
A Phase 2 Study to Evaluate Subcutaneous Abatacept vs. Placebo in Diffuse Cutaneous Systemic Sclerosis- a Double-blind, Placebo-controlled, Randomized Controlled Trial (NCT02161406)	44	7.562	44	7.562

[Khanna et al \(2006\)](#) revealed that a 95% confidence interval (CI) of [-4.7, -1.7] in mRSS change from baseline to 6 months was considered a clinically meaningful change. The lower bound of this 95% CI, -4.7, has been taken as the expected treatment difference in the sample size calculation of this study, assuming guselkumab can achieve a clinically meaningful change in most of guselkumab-treated participants.

Assuming an SD of 8 points, an 80% power at a 2-sided significance level of 0.20, with a 1:1 randomization ratio, to detect a treatment effect of -4.7 points, a total of at least 54 participants will be required.

Allowing for up to 2 participants randomized but without postbaseline efficacy assessments, approximately 56 (28 each) randomized participants are planned. In order to evaluate the interobserver and intraobserver variability of the mRSS to support Phase 3 planning, it is desirable for each center to randomize 3 participants at least.

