5.1.1. Level of Significance

As a PoC study, a 2-sided alpha of 0.2 is allocated for all hypothesis testing throughout the study. As the reference of the internal GO/NO-GO decision making, 95% CIs as well as 80% CIs will be provided for primary endpoint analysis and secondary endpoint analysis.

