5.5.2. Analysis Methods

The analyses of exploratory efficacy endpoints will be based on the FAS.

Descriptive statistics, such as n, mean, SD, median, IQ range, minimum and maximum for continuous variables and counts and percentages for discrete variables will be used to summarize data when applicable. The analysis will be based on the observed data; therefore, no imputation of missing data will be performed.

All statistical testing will be performed between treatment groups at the 2-sided 0.2 significance level.

Continuous efficacy endpoints collected at multiple post baseline time points (ie, the endpoints of change from baseline) will be compared using a MMRM model. The model will include all available data through Week 24 (for endpoints at Week 24) or through Week 52 (for endpoints at Week 52).

The explanatory variables of the MMRM model will include treatment group, baseline value of the endpoint, stratification factors (presence of ILD, baseline mRSS and baseline anti-topoisomerase I antibody status), visit, treatment group by visit interaction, and baseline value of the endpoint by visit interaction as fixed effects. The estimates of the treatment difference between treatment groups will be provided by the difference in LSMs. The 80% CI for the differences in LSMs will be calculated based on the MMRM.

The analysis of change from baseline in fibrotic change assessed with HRCT at Week 24 and nailfold capillaries change at Week 24 will be performed using ANCOVA (analysis of covariance) model with baseline value of the endpoint as covariate, and stratification factors (presence of ILD, baseline mRSS and baseline anti-topoisomerase I antibody status) and treatment group as factors.

A logistic regression model will be used to compare the proportion of participants achieving selected endpoints (eg, worsening of % predicted FVC) between guselkumab and placebo. The analyses will include treatment group, stratification factors (presence of ILD, baseline mRSS and baseline anti-topoisomerase I antibody status) as factors. The same intercurrent events and composite strategy defined in Section 5.4.2.2 will be applied to following endpoints as well:

- The proportion of participants who experience FVC decline compared with baseline through Week 52
- The proportion of participants who experience worsening of FVC through Week 52

A summary of baseline values and change from baseline at Week 24 and Week 52 will be presented for nailfold capillaroscopy.

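### The logistic models for the binary endpoints have no named test and no rule for separation, so an arm without worsening events can leave the odds ratio and its confidence interval undefined

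*SAP*

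**What the plan says.** SAP 5.4.2.3 specifies, for the binary secondary endpoints, "a logistic regression model that includes factors for treatment group and stratification factors". The factors are presence of ILD, baseline mRSS (low or high) and anti-topoisomerase I status. The model is to "provide the odds ratios, p-values, as well as the 2-sided 80% and 95% CIs for comparisons between guselkumab and placebo". SAP 5.5.2 carries the approach over to the exploratory endpoints: "A logistic regression model will be used to compare the proportion of participants achieving selected endpoints", adjusted for the same three factors.

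Neither section says whether the p-value is Wald, likelihood-ratio or exact, or what happens if the fit separates. For the MMRM, 5.4.2.3 does list alternative covariance structures, in order, for use if the model fails to converge.

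Other text that bears on the point:

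- SAP 5.4.2.2 makes the odds ratio the population-level summary for mRSS worsening at Weeks 24 and 52. Its composite strategy counts intercurrent events as worsening, and at Week 52 these include starting rescue medication.
- SAP 5.4.2.1 defines worsening as a rise of at least 5 points and at least 20%.
- SAP 5.1.1 states that "a 2-sided alpha of 0.2 is allocated for all hypothesis testing throughout the study", and offers the 80% and 95% intervals for primary and secondary endpoints as a reference for the internal go/no-go decision.
- SAP 5.1.2 rules out imputation before analysis, so the analysed number per arm can only fall below 28.

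**The concern.** Ordinary logistic regression has no finite solution when one arm, or certain combinations of arm and stratum, contains no events. The likelihood keeps rising as the coefficient runs off to infinity. Software then reports an extreme odds ratio with an enormous standard error, and a Wald test built on that ratio cannot reject.

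The failure runs in an awkward direction. The better guselkumab does on worsening, the likelier an empty guselkumab arm. In such a trial the plan as written gives no usable estimate or Wald interval for a secondary endpoint whose intervals are meant to inform the development decision, although the raw counts may favour the drug clearly.

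**Working it through.** **The plan's own figure.** SAP 3 gives a target difference of -4.7 points and a minimum total of 54. Its other inputs are these: "Assuming an SD of 8 points, an 80% power at a 2-sided significance level of 0.20, with a 1:1 randomization ratio". Per arm, n = 2 × (1.2816 + 0.8416)² × 8² / 4.7² = 26.1, rounded up to 27, so 54 in total. This reproduces the plan. With the allowance for missing post-baseline data, "approximately 56 (28 each) randomized participants are planned".

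**Implied worsening rates.** Neither document states one. Baseline mRSS is 10 to 22, so 20% is at most 0.20 × 22 = 4.4 points and the 5-point rule decides. Taking normally distributed change with SD 8, placebo mean m (assumed) and guselkumab mean m - 4.7, the rate is 1 - Φ((c - mean)/8). The cut c is 4.5 with a continuity correction, because mRSS is an integer score, and 5 without it. The chance of an empty guselkumab arm is (1 - p)^28.

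| Assumed placebo mean m | Placebo / guselkumab rate, c = 4.5 | Empty arm | Placebo / guselkumab rate, c = 5 | Empty arm |
|---|---|---|---|---|
| 0 | 28.7% / 12.5% | 2.4% | 26.6% / 11.3% | 3.5% |
| -2 | 20.8% / 8.1% | 9.5% | 19.1% / 7.2% | 12.4% |
| -3 | 17.4% / 6.4% | 16% | 15.9% / 5.6% | 20% |
| -4 | 14.4% / 4.9% | 24% | 13.0% / 4.3% | 29% |

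Example, m = -3 and c = 4.5: p = 1 - Φ(12.2/8) = 0.064, and (1 - 0.0636)^28 = 0.16.

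**Simulation of the four-term model.** Each setting used 1,000 trials with 28 per arm, mainly with assumed stratum prevalences of 60%, 40% and 40%, and separation was detected by linear programming. An infinite treatment odds ratio occurred in about 2–4% of trials at m = 0 and in up to about 34% at m = -4. Separation of any kind is more frequent (4.4% against 2.1% at 28.7%/12.5%, and 40% against 24% at 15%/5%). The excess is separation on a stratum factor alone, which leaves the treatment odds ratio finite, so the lower figures are the relevant ones.

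**Sensitivity to other assumptions.**

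- If placebo worsens by a mean of 2, the rates are 38% and 18%, and an empty guselkumab arm has probability 0.3%.
- One reference trial in SAP 3 has SDs of 4.4 to 4.6. At SD 4.5 and m = 0 the rates are 16% and 2%, and the probability is 56%.
- If 5% of participants not otherwise worsening had a composite event (assumed), each empty-arm figure is multiplied by 0.95^28 = 0.24. It falls from 2.4% to 0.6% at m = 0, and from 16% to 4% at m = -3.

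**Worked table, 0/28 against 6/28, treatment only.**

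- Wald: coefficient diverges, p = 1.000.
- Likelihood ratio: 2 × (-14.55 + 19.07) = 9.04 on 1 df, p = 0.0026.
- Fisher: 2 × C(28,6)/C(56,6) = 2 × 376,740/32,468,436 = 0.023.
- Firth: for a 2×2 table this adds 0.5 to each cell, so OR = (0.5/28.5)/(6.5/22.5) = 0.061; penalised likelihood-ratio p = 0.009.

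In the simulated trials where the treatment term separated, no Wald p fell below 0.20. The likelihood-ratio p did so in 94–100% of them at placebo rates of 15% or more.

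**The case against.** A reader might infer that the planned model will often break down. The documents do not support that. They give no worsening rate and no expected placebo change. At a placebo mean of 0, the plan's SD and difference imply about 11 events and a 2–4% risk. The larger figures need an assumed placebo improvement or a smaller SD. Protocol inclusion criterion 11 selects participants with recent skin progression, which argues against assuming a large placebo improvement. Composite events also raise the counts, most of all at Week 52 when rescue use is included, so the two visits are not equally exposed. All of this stands, and it limits the frequency.

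A reader might also infer that the SAP commits to a p-value near 1. It does not: that is a property of the Wald test, and no test is named. The omission is part of the gap.

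Nor must a substitute method be chosen after unblinding. Protocol 6.3 keeps sponsor personnel blinded until the Week 52 lock, and Protocol 9.4 has the SAP finalised before each lock, so a low pooled count could prompt a blinded change. That is an opportunity; nothing in the SAP requires anyone to take it.

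Finally, the consequence is bounded. SAP 2 rests success on the primary endpoint, SAP 5.4.1 makes the other p-values nominal, and SAP 5.6 plans descriptive statistics and listings, so a 0 against 6 split would be seen. Sparsity has not been shown for ACR CRISS or for any decline in FVC.

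**Conclusion.** The gap is real and minor. The SAP plans a four-term logistic model in 56 participants, promises an odds ratio with two intervals, and does not say how they are obtained if an arm has no events. The chance that the treatment odds ratio is infinite for mRSS worsening is about 2–4% at an assumed placebo mean change of 0, about 16–20% at -3 and about 24–34% at -4. These figures assume SD 8, a difference of -4.7, normally distributed change, 28 analysed per arm and no composite events; such events would lower them, especially at Week 52. In the affected trials a Wald analysis would miss differences that other standard methods detect at the plan's 0.20 level. The primary proof-of-concept test is untouched.

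**What to change.** In SAP 5.4.2.3 and 5.5.2, pre-specify Firth penalised-likelihood logistic regression for mRSS worsening and the other sparse binary endpoints. Keep the same treatment and stratification terms, and report profile-likelihood 80% and 95% intervals and penalised likelihood-ratio p-values. Alternatively, keep ordinary logistic regression, name its test and interval type, and state that the Firth analysis replaces it for any binary endpoint where separation occurs.

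Protocol 9.4.3 asks only for a logistic model and leaves the details to the SAP, so either wording fits it. The cost is one SAP sentence and one software option. The statistical price is mild shrinkage of the odds ratio toward 1. The change should be made before the Week 52 lock, while the sponsor is still blinded.

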5.5. Tertiary/Exploratory Efficacy Endpoints Analysis

The exploratory efficacy endpoints are listed as follows:

- Time to disease worsening: increase from baseline ≥ 5 and $\geq 20\%$ in mRSS or decrease $>10\%$ from baseline in FVC %
- The proportion of participants who experience FVC decline compared with baseline at Week 24 and Week 52
- The proportion of participants who experience worsening of FVC at Week 24 and Week 52
- Change from baseline in fibrotic change assessed with high-resolution computed tomography (HRCT) at Week 24 and Week 52 in participants with baseline fibrosis/fibrotic changes, including:

- 1) Change from baseline in quantitative lung fibrosis (QLF) score by whole lung and each lobe at Week 24 and Week 52 in participants with baseline QLF score of whole lung >0.
- 2) Change from baseline in quantitative interstitial lung disease (QILD) score by whole lung and each lobe at Week 24 and Week 52 in participants with baseline QILD score of whole lung >0.
- 3) Change from baseline in the absolute volume of consolidation, emphysema-like, ground glass, honeycombing, normal lung, reticulation texture pattern by whole lung and each lobe at Week 52.
- The proportion of participants who experience worsening of fibrotic change assessed with HRCT at Week 24 and Week 52, including:
 - 1) The proportion of participants who experience worsening of fibrotic change by whole lung and each lobe assessed with QLF of HRCT at Week 24 and Week 52, in participants with baseline QLF score of whole lung >0.
 - 2) The proportion of participants who experience worsening of fibrotic change by whole lung and each lobe assessed with QILD of HRCT at Week 24 and Week 52, in participants with baseline QILD score of whole lung >0.
- Change from baseline in frequency scale for the symptoms of gastroesophageal reflux disease (FSSG) score at Week 24 and Week 52
- Assessment of nailfold capillaries at Week 24 and Week 52, including:
 - 1) Change from baseline in average total number of capillaries/ length of nailfold; average total number of capillaries/ length of nailfold = sum (total number of capillaries of each finger) / sum (length of nailfold of each finger)
 - 2) Change from baseline in average number of enlarged capillaries (20-50 μ m)/ length of nailfold; average number of enlarged capillaries (20-50 μ m)/ length of nailfold = sum (Number of enlarged capillaries (20-50 μ m) of each finger) / sum (length of nailfold of each finger)
 - 3) Change from baseline in average Number of giant capillaries (>50 μ m)/ length of nailfold; average Number of giant capillaries (>50 μ m)/ length of nailfold = sum (Number of giant capillaries (>50 μ m) of each finger) / sum (length of nailfold of each finger)
 - 4) Change from baseline in average total number of abnormal formed capillaries/ length of nailfold; average Total number of abnormal formed capillaries/ length of nailfold = sum (Total number of abnormal formed capillaries of each finger) / sum (length of nailfold of each finger)
 - 5) Change from baseline in average number of nailfold bleeding/ length of nailfold; average Number of nailfold bleeding/ length of nailfold = sum (Number of nailfold bleeding of each finger) / sum (length of nailfold of each finger)
 - 6) Change from baseline in capillary pattern (shift table, based on worst capillary pattern)
 - 7) Change from baseline in average Blood velocity (mm/s)

- Change from baseline in patient global assessment (PGA) at Week 24 and Week 52
- Change from baseline in physician global assessment (PhGA) at Week 24 and Week 52

And LTE efficacy endpoints:

- Change from baseline and Week 52 in mRSS at Week 76 and Week 104
- The proportion of participants who experience worsening of mRSS at Week 76 and Week 104
- The proportion of participants achieving a score of 0.6 in ACR CRISS at Week 76 and Week 104
- Change from baseline in FVC and percent predicted FVC at Week 76 and Week 104
- The proportion of participants who experience worsening of FVC at Week 76 and Week 104
- Change from baseline in the measured absolute DLCO and the derived percent predicted DLCO at Week 76 and Week 104
- Change from baseline in digital ulcer counts at Week 76 and Week 104
- Change from baseline in fibrotic change assessed with HRCT at Week 76 and Week 104 in participants with baseline fibrosis/fibrotic changes, including:
 - 1) Change from baseline in QLF score by whole lung and each lobe at Week 76 and Week 104 in participants with baseline QLF score of whole lung >0.
 - 2) Change from baseline in QILD score by whole lung and each lobe at Week 76 and Week 104 in participants with baseline QILD score of whole lung >0.
- The proportion of participants who experience worsening of fibrotic change assessed with HRCT at Week 76 and Week 104, including:
 - 1) The proportion of participants who experience worsening of fibrotic change by whole lung and each lobe assessed with QLF of HRCT at Week 76 and Week 104, in participants with baseline QLF score of whole lung >0.
 - 2) The proportion of participants who experience worsening of fibrotic change by whole lung and each lobe assessed with QILD of HRCT at Week 76 and Week 104, in participants with baseline QILD score of whole lung >0.
- Change from baseline in Frequency Scale for the FSSG score at Week 76 and Week 104

